The primary endpoints of the trial will be clinical endpoints (safety, 6 month PFS, and objective response rates). All subjects will undergo radiographic imaging (CT of abdomen and pelvis and bone scan) prior to treatment, and at 3-month intervals (or as clinically indicated). Radiographic disease progression and response will be defined using PCWG2 published criteria [65], and as detailed in Section 7. Based on the prior trials leading to the approval of sipuleucel-T, and because immune therapies are expected to require up to several months before radiographic responses or stabilization might be observed, the radiographic studies obtained at 3 months will not be used to define progression, rather will be used as the baseline for future comparison. That is, while baseline studies will be obtained prior to study registration, and radiographic progression may be expected in 50% of patients at 3 months, this will not be used to define progression necessitating patients come off study, rather disease progression occurring after this initial 3-month period. These criteria, in addition to being more standard for contemporary clinical trials in advanced prostate cancer, were also specifically designed to capture late radiographic objective responses that have been observed with immune-based therapies, including pembrolizumab and other T-cell checkpoint inhibitors [80]. Time to progression will be determined from registration for all subjects. 6-month progression-free survival will be calculated for each treatment arm, as well as the median progression-free survival.

The primary endpoint for the extended treatment Arms 3 and 4 will be time to radiographic progression.

7. Measurement of Effect (PCWG2 Recommendations)

A. Malignant Disease Evaluation

To assess objective response, it is necessary to estimate the overall tumor burden at baseline (for purposes of comparison, “baseline” imaging will be that obtained at 3-month time point) to which subsequent measurements will be compared. Measurable disease is defined by the presence of at least one measurable lesion.

All measurements should be recorded in metric notation by use of a ruler or calipers. The same method of assessment and the same technique should be used to characterize each identified lesion at baseline and during follow-up. All pre-treatment evaluations should be performed as closely as possible to the beginning of treatment and not more than four weeks before registration.

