A total sample size of 20 evaluable patients is proposed for the extended treatment Arm 3 to evaluate the median time to radiographic progression. The proposed concurrent administration schedule will be considered as ineffective if it results in a median time to radiographic progression of 3 months or less. Hence, the null hypothesis that the median time to radiographic progression is at most 3 months will be tested against the alternative hypothesis that the median is greater than 3 months. A median time to radiographic progression of 6 months or more, on the other hand, will be considered as promising to warrant further clinical evaluation of the proposed concurrent administration schedule. With the proposed sample size of 20 evaluable patients for the extended treatment Arm 3, a median time to radiographic progression of 6 months will be detected with 90% power at the one-sided 0.05 significance level, assuming an accrual period of 12 months with a uniform accrual pattern and a minimum follow-up period of 12 months. Furthermore, a total sample size of 20 evaluable patients is also proposed for the extended treatment Arm 4, to evaluate the median time to radiographic progression for this study arm. The null hypothesis that the median time to radiographic progression is at most 3 months will be tested against the alternative hypothesis that the median is greater than 3 months. With the proposed sample size of 20 evaluable patients for the extended treatment Arm 4, a median time to radiographic progression of 6 months will be detected with 90% power at the one-sided 0.05 significance level, assuming an accrual period of 12 months with a uniform accrual pattern and a minimum follow-up period of 12 months. Furthermore, the proposed sample size of 20 patients for both Arm 3 and Arm 4 is adequate to estimate toxicity rates within each arm with sufficient accuracy. Specifically, toxicity rates will be estimated with a standard error of less than 12% and the corresponding two-sided 95% confidence intervals will be no wider than 40%.

NaF PET/CT will be obtained in 6 - 10 patients with known osteoblastic metastases at baseline, week 6 and week 12. This sample size will provide at least 80% power to detect moderate to large effect sizes ranging from 1.0-2.0 for the differences in SUV metrics between time points at the two-sided 0.05 significance level.

F. Analysis

F.1. General

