Subjects will be evaluated at each visit by a review of systems based on the most recent version of the NCI common toxicity criteria. Furthermore, serum chemistries, including renal function tests, blood counts, liver function tests, and serum amylase, will be evaluated at 6-12 week intervals. Toxicities will be summarized by type and severity in tabular format. Toxicity rates (grade 2, grade 3, grade 4, grade ≥ 2 , grade ≥ 3 , etc.) will be calculated for each study arm and reported along the corresponding 95% confidence intervals. The 95% confidence intervals will be constructed using the Wilson score method. Fisher's exact test will be used to compare toxicity rates between study arms. Serum chemistry and amylase parameters will be summarized using standard descriptive statistics. Changes from the baseline assessment will be evaluated using a paired t-test.

F.4.2. 6-Month Progression Free Survival Rate and Median Time to Radiographic Progression

The 6-month progression-free survival rate, along with the corresponding two-sided 95% confidence intervals, will be reported for each arm, and for the overall combined study. The Wilson

score method will be used to construct the confidence intervals. Fisher's exact test will be used to compare the 6-month progression-free survival rates between study arms.

Median time to radiographic progression will be estimated for each arm using the Kaplan-Meier method. The median time to radiographic progression will be reported for each of the four arms along with the corresponding 95% confidence intervals which will be constructed using the Brookmeyer-Crowley method. The log-rank test will be used to perform the comparison of time to radiographic progression between Arm 1 versus Arm 2. A one-sided 0.10 significance level will be used to conduct the comparison of the 6-month progression-free survival rate and time to radiographic progression between study arms. Within Arm 3 and Arm 4, the null hypothesis that the median time to radiographic progression is at most 3 months will be tested against the alternative hypothesis that the median time to radiographic progression is greater than 3 months.

In order to evaluate the 6-month progression-free rate and median time to radiographic progression as a function of baseline time point (pretreatment or 3-months post treatment, the analysis will be conducted using two different baseline values: (1) Date of randomization, and (2) 3-months disease assessment.

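### Arms 3 and 4 test a 3-month median without naming a test or allowing for 12-weekly scans, so the stated 90% power at one-sided 0.05 is not supported

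*Combined protocol and SAP*

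**What the plan says.** Section 6.B makes time to radiographic progression the primary endpoint of Arms 3 and 4. It schedules imaging "prior to treatment, and at 3-month intervals (or as clinically indicated". Section 9 places the Arm 3 and 4 scans at weeks 12, 24, 36 and 48, each with a 7-day window either side.

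Section 11.E sets the size: "A total sample size of 20 evaluable patients is proposed for the extended treatment Arm 3", and "a total sample size of 20 evaluable patients is also proposed for the extended treatment Arm 4". For each arm it states that "a median time to radiographic progression of 6 months will be detected with 90% power at the one-sided 0.05 significance level", assuming 12 months of uniform accrual and at least 12 months of follow-up.

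Section 11.F.4.2 repeats the hypothesis: "Within Arm 3 and Arm 4, the null hypothesis that the median time to radiographic progression is at most 3 months will be tested". It names no test. The only median procedure it gives is the Kaplan-Meier estimate with "95% confidence intervals which will be constructed using the Brookmeyer-Crowley method".

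On the first scan the text pulls in two directions. Sections 6.B and 7.A say the 3-month scan is not used to define progression and becomes the baseline. The note in Section 7.A also says progression from the pre-treatment scans will be documented, and Section 11.F.4.2 analyses both baselines.

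**The concern.** Progression that occurs between scans is normally dated at the scan that shows it, so a recorded time can exceed the true one by up to 12 weeks. Against a 3-month null, that delay is as large as the quantity being tested. A test built for exact times will read the delay as benefit.

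The decision at stake is whether each extended schedule is promising enough for further clinical evaluation, on 40 patients in all. With no test named, the analyst must choose one later. One candidate matches the stated power but may not hold 5%. The other is the only median method in the text, and it does not have 90% power.

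**Working it through.** **Inputs.** From Section 11.E: n = 20 per arm, null median 3 months, alternative 6 months, one-sided 0.05, 12 months accrual plus 12 months follow-up. From Section 9: scans at weeks 12, 24, 36 and 48. Assumptions not in the documents: exponential times, and progression dated at the scan that shows it. Simulated figures come from 40,000 to 60,000 trials per scenario; scan-grid runs are cut at week 48 unless stated.

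**1. Reproducing the 90%.** Under the alternative the hazard is ln 2 / 6 = 0.1155 per month. The expected event fraction is 1 - (0.25 - 0.0625)/(12 x 0.1155) = 0.865, or 17.3 events from 20 patients. Power = Phi(sqrt(17.3) x ln 2 - 1.645) = Phi(1.24) = 89%. Simulating the one-sample log-rank test on exact times gives 89% power and a 3.6% level. So the stated figure belongs to an exponential-type test on exact times.

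**2. The same test on scan dates.** Twelve weeks is 84/30.4375 = 2.76 months. With a true 3-month median, the chance of progressing in any one interval is q0 = 1 - 2^(-2.76/3) = 0.471. Recorded follow-up per event averages 2.76/0.471 = 5.85 months, against 3/ln 2 = 4.33 months for exact times. The test therefore sees an apparent median of 5.85 x ln 2 = 4.06 months when the truth is 3. Its simulated rejection rate at nominal 5% is about 30%.

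**3. How far that 30% depends on assumptions.** The same test, with a true 3-month median unless stated:

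| Scenario | Rejection rate |
|---|---|
| Exponential, all events dated at scheduled scans | about 30% |
| 25% / 33% / 50% of events dated exactly (off schedule) | 19% / 16% / 12% |
| Weibull shape 0.8 / 1.2 / 1.5 | 55% / 11% / 1% |
| True median 12 weeks (2.76 months) | about 18% |
| First countable event at week 24 | about 89% |

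**4. Brookmeyer-Crowley.** The week-12 scan, even at the end of its window (91 days = 2.99 months), falls before 3 months. The lower limit exceeds 3 months when enough of the 20 patients are progression-free at that scan. With p = x/20, the statistic (p - 0.5)/sqrt(p(1 - p)/20) is 1.41 for x = 13, 1.95 for x = 14 and 2.58 for x = 15. So x = 15 is needed at 1.96 and x = 14 at 1.645. Progression-free probabilities at 12 weeks are 0.529 (null) and 0.727 (alternative). At exactly 3 months they are 0.5 and 0.707. Binomial tails give:

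| | 95% interval (x at least 15) | One-sided 0.05 (x at least 14) |
|---|---|---|
| 12-weekly grid | level 3.7%, power 52% | level 9.4%, power 71% |
| Exact times or scans at exactly 3 months | level 2.1%, power 44% | level 5.8%, power 64% |

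**5. A test that allows for the grid.** Let x be the events and N the patient-intervals at risk. The grouped exponential score test rejects when (x - N q0)/sqrt(N q0 (1 - q0)) is below -1.645. With 20 patients and week 12 counted, its level is 4.3% and its power 87%. The Wald version gives 3.7% and 86%. If week 12 is treated as a negative scan, the score test itself rejects a true 3-month median about 27% of the time. Its level also depends on the exponential form: 18% at Weibull shape 0.8 and about 0.5% at shape 1.2.

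**The case against.** The strongest reply is that the plan never adopts the test with the inflated error. That test is inferred from a power figure, while the text names only Kaplan-Meier and Brookmeyer-Crowley, and Section 11.F.1 promises a detailed analysis plan before final analysis. This stands in part. A reader might infer that the trial has a demonstrated 30% false-positive rate; the documents do not support that. It does not rescue the 90%, which no procedure named in the text delivers.

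A reader might also infer that progression can be dated only at weeks 12, 24, 36 and 48. Section 6.B allows clinically indicated scans, and Section 7.C.5 counts death as an event. The documents give no share for these, so the 12-19% for 25-50% off-schedule dating is a range and not an estimate.

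Two other shortcuts fail. The 18% applies to a true median of 12 weeks, so it is not the lower end of a type I error range at 3 months. The 44% and 64% apply to exact times or scans at exactly 3 months, so they are not the Brookmeyer-Crowley power on the scheduled grid.

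Finally, the parametric remedy has a weakness of its own: its level holds only under the assumed distribution. That stands and must be disclosed. Midpoint dating with a one-sample log-rank test performs similarly (level 4.4%, power 87-90%), so the interval-censored model is one option among several.

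**Conclusion.** The point holds: the stated combination of 20 patients, 90% power and one-sided 0.05 is not supported for the data that these arms will produce. The test that yields 90% has about 30% type I error on scheduled scan dates under exponential times. That figure is conditional: it ranges from 1% to 55% over the Weibull shapes tried and reaches about 89% if no event can count before week 24. Brookmeyer-Crowley falls short of 90% under either scan timing examined (52-71% on the grid, 44-64% otherwise), given exponential times.

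This should be fixed before the final analysis. It is not a fatal flaw: the cohorts are non-randomised parts of a pilot, a positive result leads only to further evaluation, and 20 patients remain nearly enough with a suitable test.

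**What to change.** In Section 11.F.4.2:

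- Name a one-sided 0.05 test that allows for the scan grid. One example is an interval-censored exponential model (last negative to first positive scan, actual dates) against a 3-month median.
- Reconcile Sections 6.B and 7.A with 11.F.4.2 by stating, for each of the two baselines, whether progression at week 12 against the pre-treatment scan is an event. In the pre-treatment-baseline analysis it must count, because otherwise the proposed test has about 27% type I error. This concerns the endpoint only and leaves the treatment rules untouched.
- Report the Kaplan-Meier and Brookmeyer-Crowley results and a Weibull-shape sensitivity analysis alongside.

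In Section 11.E, restate power as about 86-87% at a level of about 4%, for the pre-treatment-baseline analysis under exponential times.

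The cost is analysis text and a standard procedure; the sample size stays at 20 per arm. Stated power falls by about 3-4 points, and the primary test comes to rest on a parametric assumption.

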ⁱ Can be +/- 7 days of this visit, and not required if this is off-study visit and previous scans already confirmed disease progression

^j CT of chest at this time point only as clinically indicated

^k PT/INR only required for those subjects who will be undergoing a biopsy. May be performed up to 30 days prior to biopsy, required same day if subject is on coumadin

^l If NaF PET/CT is available as standard of care procedure, this may be substituted for bone scan (bone scintigraphy), however all pre-treatment and post-treatment tests must use the same modality (NaF PET/CT or bone scintigraphy)

^m See section 9 for whether or not biopsy and FLT PET is required

Plan of Treatment: ARM 2

Vaccine / Treatment Visit:	SCREENING		Day 1	Day 15 (+/- 3 days)	Day 29 (14 +/- 3 days after day 15)	Day 43 (14 +/- 3 days after day 29)	Day 57 (14 +/- 3 days after day 43)	Day 71 (14 +/- 3 days after day 57)	Day 85 (14 +/- 3 days after day 71) – 3 month	Da 106 (21 +/- 3 days after day 85)	Da 127 (21 +/- 3 days after day 106)	Day 148 (21 +/- 3 days after day 127)	Day 169 (21 +/- 3 days after day 148) – 6 m	9-month F/U (84 +/- 10 days after day 169)	OF F STUDY 12-month F/U – (84 +/- 10 days after 9month F/U)
	Within 6 weeks of day 1	Within 4 weeks of day 1													
History and Physical Exam															
History	X														
Consent	X														
Physical Exam, ECOG PS		X	X			X			X	X	X	X	X	X	X
Tox assessment ^a		X	X	X	X	X	X	X	X	X	X	X	X	X	X
Lab Tests															
CBC	X		X			X			X ^g	X	X	X	X	X	X
Chemistry panel ^f	X		X			X			X ^g	X	X	X	X	X	X
PT/INR		X ^k							X ^k						
Serum testosterone	X														
PSA and PAP	X		X			X			X ^g	X	X	X	X	X	X
Procedures															
CT chest/abdomen/pelvis	X								X ^{gi}				X ^{hj}	X ^{hj}	X ^{ij}
Bone scan ^l	X								X ^g				X ^h	X ^h	X ⁱ
Leukapheresis		X ^b											X ^{bh}		
FLT PET scan ^m		X ^c							X ^g						
Tissue biopsy ^m		X ^d							X ^g						
Tetanus immunization		X ^e													
Blood for immune analyses		X				X			X ^g				X	X	X
Blood for CTC analysis		X				X			X ^g				X	X	X
Treatments															
DNA immunization			X	X	X	X	X	X							
Pembrolizumab infusion									X	X	X	X			

^a Study coordinator or research nurse review of systems

^b For patients unable to undergo leukapheresis, a 200-mL blood draw (green top tubes) may be performed instead

^c FLT PET scan – within 4 weeks (28 days) of day 1 – to provide baseline study for comparison prior to treatment

^d Biopsy within 2 weeks prior to day 1

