Patients will come off study at the time of radiographic (CT and/or bone scintigraphy) disease progression, with progression being defined only AFTER the first 3-month staging evaluation, at the time of undue toxicity (as defined below), or at the discretion of the patient and treating physician that continuing treatment is not in the best interest of the patient and/or that other standard therapies for prostate cancer are warranted due to symptomatic progression. Patients should be discouraged from discontinuing protocol treatment for PSA rise only. NaF and FLT PET/CT scans will be investigational and will not be used for making individual subject treatment decisions with respect to progression necessitating continuing or discontinuing protocol treatment. However, findings on NaF or FLT PET/CT that might pose medical risk to individual subjects will be communicated to the treating physician such that dedicated clinical imaging/intervention could be pursued, if necessary. Such findings on NaF or FLT PET/CT, by themselves, will not be used to define disease progression necessarily requiring patients to come off trial. Patients who, in the discretion of the treating physician, appear to be benefiting (e.g. declining serum PSA and/or

improvement in symptoms despite new radiographic lesions), may continue in protocol treatment/observation after discussion with the PI and study sponsor. Patients will continue to have blood drawn for immune studies, as per study calendar, up to one year after screening, even if off study prior to that time. Patients who undergo an initial research biopsy and/or NaF/FLT PET scan should also undergo the subsequent scans, as long as they are willing, even if they are off study prior to Month 3. In particular, evaluations performed at 6-month time point should be performed even if off-study prior to that time, if feasible. All subjects who have not come off study earlier for these reasons will come off study at the end of one year.

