The disappearance of all nontarget lesions and undetectable PSA tumor marker levels. To be assigned a status of complete response, changes in tumor measurements must be confirmed by repeat assessments performed **no less than four weeks** after the criteria for response are first met.

b. Incomplete Response/Stable Disease (SD)

The persistence of one or more nontarget lesion(s) and/or the persistence of detectable serum PSA tumor marker levels. To be assigned a status of stable disease, measurements must have met the stable disease criteria at least once after study entry at a minimum interval of 12 weeks.

c. Progressive Disease (PD)

The appearance of one or more new lesion(s) and/or unequivocal progression of existing nontarget lesions.

NOTE: For lesions only detectable by bone scan (or NaF PET/CT), the appearance of ≥ 2 new lesions, with symptoms, will constitute disease progression. Without symptoms, and if no other evidence of disease progression (no progressive disease by PSA or measurable disease criteria), progression must be documented with repeat bone scintigraphy (or NaF PET/CT) at least 6 weeks later demonstrating ≥ 2 new lesions. This is to eliminate the possibility of flair responses seen on bone imaging scans.

3. Symptomatic Deterioration

Patients with a global deterioration of health status requiring discontinuation of treatment without objective evidence of disease progression at that time should be classified as having symptomatic deterioration.

4. PSA Progression

While PSA values will be collected, and PSA kinetics (PSA responses and maximal changes in PSA by waterfall plots) monitored as secondary endpoints, PSA rise will not be used to determine objective disease progression. Similar to the radiographic studies above, PSA progression or response will be defined using both pre-treatment (study entry) and 3-month values as baseline values.

- a. **PSA Complete Response:** Decrease in PSA to <0.2 ng/mL and confirmed with PSA measurement a minimum of four weeks later (confirmed PSA CR). There must be no evidence of radiographic progression.
- b. **PSA Partial Response:** Greater than or equal to 50% reduction in baseline PSA. There must be no evidence of radiographic progression.
- c. **Best Response:** This is calculated from the sequence of objective statuses. The date of response will be defined as the first date at which PSA declined from baseline or normalized.

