 - i. **Confirmed PSA PR:** Two or more objective statuses of PSA PR or better a minimum of four weeks apart documented before progression. Best response for objective disease must be stable/no response or better.
 - ii. **Unconfirmed PSA PR:** One objective status of PSA PR documented before progression, but not qualifying for confirmed PSA PR. Best response for objective disease must be Stable/no response or better.
 - iii. **No PSA Response:** Objective PSA status does not qualify as a PSA PR or unconfirmed PSA PR.

iv. **Inadequate Assessment, response unknown:** When best response for objective disease is inadequate or unknown or when PSA has been inadequately assessed, then PSA response will be coded likewise.

d. **PSA Progression:** Although not considered progression per the primary objective of this study, time to PSA progression will be used for secondary analyses. PSA progression will be defined as a **50%** increase in PSA over the nadir PSA, and ≥ 2 ng/mL above the nadir, confirmed by a second value 3 or more weeks later (i.e. confirmed rising trend). If no on-study reduction has occurred, nadir would be the baseline value (pre-treatment or month 3 time point for analyses).

C. Evaluation of Patient’s Best Overall Response

The best overall response is the best response recorded from baseline until disease progression/recurrence, taking as reference for progressive disease the smallest measurements recorded after baseline. The table below provides overall responses for all possible combinations of tumor responses in target and nontarget lesions, with or without new lesions.

To be assigned a status of complete or partial response, changes in tumor measurements must be confirmed by repeat assessments performed **no less than four weeks** after the criteria for response are first met.

To be assigned a status of stable disease, measurements must have met the stable disease criteria at least once after study entry at a minimum interval of 12 weeks.

Overall Response for all Possible Combinations of Tumor Response

Target Lesions	Nontarget Lesions	New Lesions	Overall Response
CR	CR	No	CR
CR	Incomplete response/SD	No	PR
PR	Non-PD	No	PR
SD	Non-PD	No	SD
PD	Any	Yes or No	PD
Any	PD	Yes or No	PD
Any	Any	Yes	PD

CR = complete response; PR = partial response; SD = stable disease; PD = progressive disease

1. First Documentation of Response

The time between initiation of therapy and first documentation of PR or CR.

2. Confirmation of Response

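### PSA progression waives the repeat bone scan (section 7.B.2.c), so PSA decides whether unconfirmed asymptomatic bone lesions count as radiographic progression; confirmed bone progression also has no dating rule

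*Combined protocol and SAP*

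**What the plan says.** The note under section 7.B.2.c covers lesions detectable only on bone scan or NaF PET/CT. With symptoms, two or more new lesions are progression. For the rest: "Without symptoms, and if no other evidence of disease progression (no progressive disease by PSA or measurable disease criteria), progression must be documented" by repeat imaging "at least 6 weeks later demonstrating ≥ 2 new lesions". The stated purpose is to exclude flare.

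Section 7.B.4 then says "PSA rise will not be used to determine objective disease progression". Its item d, on PSA progression, adds: "Although not considered progression per the primary objective of this study, time to PSA progression will be used for secondary analyses".

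The endpoints concerned are primary. Section 6.B names 6-month PFS for the trial and time to radiographic progression for Arms 3 and 4. Section 7.C.5 runs the time to progression or death, once from randomization and once from the 3-month assessment, and section 11.F.4.2 repeats the two baselines. Neither says whether a confirmed bone progression is dated at the first or the repeat scan.

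Two neighbouring passages bear on the same event. The general nontarget rule above the note reads "The appearance of one or more new lesion(s) and/or unequivocal progression of existing nontarget lesions". Section 6.B says of the research PET scans: "Such findings on NaF or FLT PET/CT, by themselves, will not be used to define disease progression", in a sentence that goes on to speak of patients having to leave the trial.

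**The concern.** The repeat scan is required only when PSA and measurable disease both show no progression. Take two asymptomatic patients with identical new bone lesions and stable measurable disease. The one with PSA progression has an event on a single scan. The one without has an event only if a later scan confirms the lesions. The imaging is the same and the scoring differs, although the plan keeps PSA progression out of the primary objective.

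If PSA behaves differently between arms, or between this trial and the 3-month historical median used for Arms 3 and 4, part of a difference in radiographic outcome could come from PSA and not from scans. The missing dating rule determines whether PSA can also move the event date, and with it 6-month status.

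**Working it through.** **1. The rule, case by case** (two or more new lesions, bone imaging only)

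| Symptoms | Measurable-disease progression | PSA progression | Repeat scan needed? |
|---|---|---|---|
| Yes | any | any | No |
| No | Yes | any | No (already progression on measurable disease) |
| No | No | Yes | No, by implication |
| No | No | No | Yes, at least 6 weeks later |

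Only the last two rows differ by PSA. PSA progression itself needs a confirming value 3 or more weeks later (section 7.B.4.d).

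**2. Dates.** Inputs: 6-month visit at Day 169, scans within 7 days (section 9.Q); repeat at least 6 weeks = 42 days; imaging every 3 months (section 6.B), with no 6-week repeat in the calendars.

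- Earliest confirmation: 169 + 42 = Day 211 (162 + 42 = 204 to 176 + 42 = 218 with the scan window).
- At the next scheduled scan: 169 + 84 = about Day 253.

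What follows depends on choices that the plan leaves open or makes twice:

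- Month 3 scan as reference, clock from randomization or registration, event dated at the repeat: Day 211 is past 6 months, so 6-month status differs by PSA.
- Same, but dated at the first scan: the shift is 0 days. PSA still decides whether confirmation is needed.
- Clock from the 3-month assessment: 6 months ends at about Day 253 to 268 (85 + 168 to 85 + 183). Day 211 is inside, so this example does not change status.
- Pre-treatment scan as reference: lesions new at Day 85 can be confirmed at the scheduled Day 169 scan, 84 days later.

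**3. Size in Arms 1 and 2.** The plan's figure first. Power is the sum of Bin(x; n, p1) × Bin(y; n, p2) over all outcomes with one-sided Fisher p ≤ 0.10. For 25% vs 70% this gives 0.782 at n = 14 and 0.823 at n = 15; for 20% vs 65% at n = 15 it gives 0.827. The stated 15 per arm reproduces.

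One reclassified patient moves an arm's rate by 1/15 = 6.7 points, against a design difference of 45 points.

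Illustration only, because the documents do not give the share affected. Let true 6-month PFS be 25% in both arms, let a share f of Arm 1 failures be deferred past 6 months and none in Arm 2. Arm 1's apparent rate is 0.25 + 0.75f.

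| f | Apparent Arm 1 rate | Chance of a false positive |
|---|---|---|
| 0 | 0.250 | 0.042 |
| 0.10 | 0.325 | 0.101 |
| 0.20 | 0.400 | 0.201 |
| 0.30 | 0.475 | 0.342 |

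If Arm 2 is affected too, the effect shrinks: with f = 0.20 in Arm 1 and 0.10 in Arm 2 the chance is 0.102.

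**4. Size in Arms 3 and 4.** With 20 patients, exponential times, 12 months' accrual and 12 months' further follow-up, λ = ln 2 / 6 and expected events = 20 × [1 − (e^(−12λ) − e^(−24λ)) / (12λ)] = 17.3. Power ≈ Φ(ln 2 × √17.3 − 1.645) = 0.89, against a stated 0.90. With a true median of 3 months and 0, 10, 20, 30 or 50% of patients dated 42 days late, a one-sample log-rank test at one-sided 0.05 (assumed; the plan names no test) rejects in about 0.036, 0.047, 0.058, 0.075 and 0.116 of simulated trials. The shares are again assumptions.

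**The case against.** The best defence is that the PSA exclusion means PSA by itself. Section 6.B discourages stopping treatment for a PSA rise only, and section 7.C.6.b says the marker alone will not be used to assess response. Under the note, two or more new bone lesions are always required; PSA only waives a confirmation step, as symptoms or measurable-disease progression also do. This stands as a limit on scope: PSA never creates an event. It does not remove the contradiction, because the waiver still makes PSA part of the definition of a radiographic event.

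A reader might go further and infer that PSA sets the progression date and turns 6-month failures into successes. The documents do not support that without conditions. It needs dating at the repeat scan, the Month 3 reference and a clock from randomization or registration. The phrase about first objective documentation in section 7.C.3 points towards the repeat scan, but it defines duration of response, not time to progression.

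Nor do the PSA figures in section 2.F show a bias between Arms 1 and 2. They concern any decline (8 of 13 in Arm 1), not confirmed PSA progression, and the comparison is with the non-randomized Arm 3.

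Two side conflicts might also be inferred, and both are minor. The one-lesion and two-lesion rules can be read together, since the note is a specific exception to the general rule. The NaF sentence in section 6.B concerns coming off trial and scans called investigational, whereas footnote l in the Arm 1 and 2 calendars concerns NaF as a standard-of-care substitute for the bone scan. It does not show that such patients lack a progression event.

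**Conclusion.** The point holds in limited form. The note and the PSA statements contradict each other, and nothing in the plan reconciles them. The effect is confined to asymptomatic patients with new lesions on bone imaging alone and no measurable-disease progression. In them, PSA decides whether unconfirmed lesions count in the radiographic endpoints.

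A change in 6-month status is conditional on the three choices named above. Where they hold, each such patient moves the rate by 6.7 points at 15 per arm. The number of such patients is unknown, so the false-positive figures show sensitivity to assumed shares and are not estimates. The lack of a dating rule is a gap whichever reading is taken. This should be fixed.

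**What to change.** For endpoint scoring only:

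- Remove the PSA condition from the note in section 7.B.2.c. Asymptomatic bone-only lesions without measurable-disease progression then need the same repeat-scan confirmation whatever the PSA. The next scheduled scan at least 6 weeks later may serve. Leave the symptom route as it is.
- State in section 7.C.5 that confirmed bone progression is dated to the first scan showing the lesions.
- State a default for patients with no later scan, for example counting the first scan as the event, with a sensitivity analysis using the opposite default.
- Add a cross-reference from the New Lesions column of the response table in section 7.C to the two-lesion bone rule.
- Clarify that the NaF sentence in section 6.B refers to investigational NaF scans, not to NaF substituted for the bone scan under footnote l.

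The cost is wording. The sample size does not change, and no visits are added if the next scheduled scan can confirm. The downside is that a few patients with PSA progression are confirmed only at a later scan. Off-study rules are a separate matter, which the sponsor should reconcile with these passages.
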